	
approximately 19 weeks, comprising a screening & baseline period (3 weeks), 12 weeks of double-blind treatment and then a final follow up visit, 4 weeks after the end of the treatment period. There will be a total of 8 visits whilst participating in the study.
 
Subjects who provide informed consent will be screened for participation in the study. After giving informed consent, but before Screening Visit 2 (i.e. before starting the placebo run-in period), subjects will be withdrawn from prohibited concomitant medications.
 
At the first visit (Screening Visit 1), they will be provided with a paper diary, which they will be asked to complete once daily (prior to retiring to bed) for 7 days, recording their recall of the total number of hot flushes (also known as hot flashes) over the previous 24 hours, and the severity of each of those hot flushes. At the second visit (Screening Visit 2), the investigator or designee will review the paper diary to determine if the subject can continue in the study. To continue, subjects must have completed the paper diary for at least 6 days and recorded an average of at least 8 moderate or severe hot flushes per day over the last 5 days that the paper diary was completed.
 
Subjects who continue to satisfy all the initial selection criteria at Screening Visit 2 will commence placebo treatment on a single-blind (subject only) basis and be provided with an electronic diary (eDiary) which they will be asked to complete twice a day for 14 (<math>\pm 2</math>) days during the remaining screening/baseline period. The eDiary will record the subject's recall of the number of hot flushes during the day (recorded just prior to retiring to bed) and overnight (recorded on waking). The severity of each hot flush will also be recorded. To proceed to randomisation, the subject will be required to have completed the eDiary for at least 9 days and to have recorded an average of at least 7 moderate or severe hot flushes per day over the last 7 days that the eDiary was completed.
 
At the baseline visit (Day 1), subjects who comply with all selection criteria will be enrolled into the 12-week double-blind portion of the study and be randomised to one of the NT-814 doses or placebo. Subjects who do not meet the eDiary criteria will not continue into the study (they will be screen failures).

--	--

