
 
Hot Flush Related Daily Interference Scale (HFRDIS) completed at all visits except Screening
 
	
 
Change from baseline in the HFRDIS scores at Weeks 2, 4, 8, 12 and 16
 

 
Menopause-Specific Quality of Life Intervention Version (MenQoL-I) completed at Baseline and Weeks 4, 8, 12 and 16
 
	
 
Change from baseline in the MenQoL-I scores at Weeks 4, 8, 12 and 16
 

 
Beck Depression Inventory (Version II) completed at all visits except Screening
 
	
 
Change from baseline in the Beck Depression Inventory II scores at Weeks 2, 4, 8, 12 and 16
 

SAFETY ASSESSMENTS	SAFETY ENDPOINTS

 
Adverse events recorded throughout the study (from Screening Visit 2 to Week 16)
 
	
 
Number of treatment emergent adverse events
 
Number of treatment emergent serious adverse events
 
Number of treatment emergent adverse events resulting in treatment discontinuation
 
Severity of treatment emergent adverse events
 
Number of treatment emergent related adverse events
 

 
Physical Examination recorded at Screening Visit 2, Baseline and Week 16
 
	
 
Treatment emergent changes in physical examination will be recorded as adverse events
 

 
Weight recorded at each visit (except Screening Visit 1) and height at Screening Visit 2
 
Waist circumference recorded at each visit (except Screening visits 1 and 2)
 
	
 
Change from baseline in weight at Weeks 2, 4, 8, 12 and 16
 
Change from baseline in body mass index at Weeks 2, 4, 8, 12 and 16
 
Change from baseline in waist circumference at Weeks 2, 4, 8, 12 and 16
 

 
Electronic Columbia Suicide Severity Rating Scale (eC-SSRS) recorded at
 
	
 
Change from baseline in eC-SSRS at Weeks 4, 12 and 16
 

Baseline and Weeks 4, 12 and 16
	

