Subjects who withdraw or are withdrawn from participation in the study should attend an Early Termination visit at which the procedures scheduled for the final Follow Up visit will be undertaken. If the subject withdraws due to an AE, the event should be followed until resolution or care is transferred to the subject's usual physician.

Subjects who are withdrawn after randomisation will not be replaced.

In some circumstances, the Investigator may discontinue study treatment without the need to withdraw the subject from participation in the study. When subjects permanently discontinue IMP, effort should be made to continue following the subject through to the end of scheduled visits for safety and to obtain efficacy assessments that can be assigned to the originally randomised treatment.

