### **8.6.4 Screening Visit 2**

Subjects will return to the clinic for Screening Visit 2, during which the investigator or designee will review the paper diary to determine if the subject can continue in the study. To continue, subjects must have completed the paper diary for at least 6 days and have recorded an average of at least 8 moderate or severe hot flushes per day over the last 5 days that the paper diary was completed.

Subjects who **do not** record an average of at least 8 moderate or severe hot flushes per day (including night-time) over the last 5 days that the paper diary was completed, or who are not compliant with diary completion will be Screen Failures and will not be able to continue into the study. Limited data will be collected for subjects who withdraw from the study after providing informed consent but prior to randomisation onto the study (Screen Failures).

If the diary compliance and hot flush criteria **are** satisfied, the following assessments will be performed to further determine the subject's eligibility for inclusion into the study:

- Review of other inclusion/exclusion criteria
- Full physical examination, 12-lead ECG, vital signs
- Blood sampling for haematology and clinical chemistry, and urine sample collection for urinalysis and urine pregnancy test
- Review for adverse events and changes in concomitant medications

Subjects who continue to satisfy selection criteria will be provided with, and trained on the use of, an eDiary to be completed twice a day, starting the evening of Screening Visit 2 and continuing until they return to the site for the Baseline visit. Each evening, subjects will record in the diary the total number of hot flushes of each severity experienced that day since waking. Each morning upon waking, subjects will record the number of times they woke up in the night and the total number of hot flushes of each severity experienced during the night.

At Screening Visit 2, subjects will commence placebo treatment. Their first dose of placebo will be taken in the clinic and all subsequent doses at home once a day in the evening (starting the following day) up until the day before the Baseline visit. Subjects will be provided with a medication kit containing sufficient placebo capsules for a 2-week period (plus 2 days overage).

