### **10.5 Adverse events**

#### **10.5.1 Definitions**

##### **Adverse Event (AE)**

Any untoward medical occurrence in a subject or clinical trial subject administered an IMP and which does not necessarily have a causal relationship with this treatment. An AE can therefore be any unfavorable and unintended sign (including an abnormal laboratory finding, for example), symptom, or disease temporally associated with the use of an IMP, whether or not considered related to the IMP.

---

As the full medical history and physical evaluation does not take place until Screening Visit 2, the adverse event reporting period starts after this visit is complete.

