#### **10.5.4 Adverse Event Reporting**

Adverse events may be volunteered spontaneously by the subject, or discovered as a result of general, non-leading questioning. As the full medical history and physical evaluation does not take place until Screening Visit 2, the adverse event reporting period starts after this visit is

complete. Adverse events occurring from the time of Screening Visit 2 up to the final study visit will be recorded. All AEs should be recorded in the eCRF and in the subjects' source notes.

Any SAE occurring from Screening Visit 2 until 28 days after the last dose of IMP must be reported immediately (within 24 hours of the investigator becoming aware of it) and recorded on the SAE Form. Detailed instructions for the reporting of SAEs can be found in the Study Manual. All subjects with a SAE must be followed up and the outcomes reported. The investigator must supply the Sponsor and the relevant agency/IRB/IEC with any additional requested information (e.g., autopsy reports and terminal medical reports). Any follow-up information on a previously reported SAE will also be reported within 24 hours of awareness.

If the Investigator does not have all information regarding an SAE, he/ she will not wait to receive additional information before reporting the event and completing the appropriate data collection form. The Investigator should always provide a preliminary assessment of causality at the time of the initial report as described in Section 10.5.3.

The primary mechanism for reporting SAEs will be a paper collection form.

Scan & email of the SAE form is the preferred method to transmit this information to the project contact for SAE receipt although fax transmission is also acceptable. In rare circumstances and in the absence of email facilities or fax equipment, notification by telephone is acceptable, with a copy of the SAE data collection form sent by overnight mail. Initial notification via the telephone does not replace the need for the Investigator to complete and sign the SAE data collection form within the designated reporting periods.

If required according to local regulatory authorities and IRB/IEC policy, each Investigator must then notify his or her relevant agency/IRB/IEC of the SAE.

NeRRe is required to expedite to worldwide regulatory authorities reports of SUSARs in line with the relevant legislation. Fatal or life-threatening SUSARs must be reported within 7 calendar days and other SUSARs within 15 calendar days.

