- Listing 16.2.7.4 All Treatment-Emergent Adverse Events Leading to Treatment Discontinuation (Safety Analysis Set)
- Listing 16.2.7.5 All Treatment-Emergent Adverse Events Leading to Study Discontinuation (Safety Analysis Set)
- Listing 16.2.7.6 All Treatment-Emergent Adverse Events Leading to Death (Safety Analysis Set)
- Listing 16.2.7.7 Pre-Treatment Adverse Events (Safety Analysis Set)

*Listing of Individual Laboratory Measurements by Subject (CSR Appendix 16.2.8)*

- Listing 16.2.8.1 Laboratory Results: Hematology (Safety Analysis Set)
- Listing 16.2.8.2 Laboratory Results: Chemistry (Safety Analysis Set)
- Listing 16.2.8.3 Laboratory Results: Urinalysis (Safety Analysis Set)
- Listing 16.2.8.4 Laboratory Results: Bone Turnover Markers (Safety Analysis Set)
- Listing 16.2.8.5 Overall Abnormal Clinically Significant Assessment for Laboratory Parameters (Safety Analysis Set)

- Listing 16.2.8.6 Description of Abnormal Assessments for Laboratory Parameters (Safety Analysis Set)
- Listing 16.2.8.7 Urine Pregnancy Test (Safety Analysis Set)
- Other Safety Data (CSR Appendix 16.2.9)*
- Listing 16.2.9.1.1 Vital Signs (Safety Analysis Set)
- Listing 16.2.9.1.2 Description of Abnormal Assessments for Vital Signs (Safety Analysis Set)
- Listing 16.2.9.2 Physical Examination (Safety Analysis Set)
- Listing 16.2.9.3.1 Electrocardiograms (Safety Analysis Set)
- Listing 16.2.9.3.2 Description of Abnormal Assessments for Electrocardiograms (Safety Analysis Set)
- Listing 16.2.9.4 C-SSRS (Safety Analysis Set)
- Listing 16.2.9.5 Prior Medications (Safety Analysis Set)
- Listing 16.2.9.6 Concomitant Medications (Safety Analysis Set)
- Listing 16.2.9.7 Concomitant Non-Drug Treatments (Safety Analysis Set)

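### Events between consent and Screening Visit 2, including those after protocol-required medication withdrawal, fall outside AE and SAE reporting; the 24-hour SAE duty can end before follow-up does, and the SAP listings omit run-in events in women never given double-blind drug

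*Protocol*

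**What the plan says.** **Before Screening Visit 2.** The synopsis states that after consent and before this visit "subjects will be withdrawn from prohibited concomitant medications". Protocol Section 8.6.3 sets a minimum of 6 days between the two screening visits and lets the interval be lengthened for washout.

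**Opening of the window.** Under the AE definition in Section 10.5.1, "the adverse event reporting period starts after this visit is complete". The reason given is that the full history and examination are not done until then. Section 10.5.4 repeats that sentence and then adds: "Adverse events occurring from the time of Screening Visit 2 up to the final study visit will be recorded". The synopsis has "Adverse events recorded throughout the study (from Screening Visit 2 to Week 16". Section 8.6.4 places two things inside the visit: an AE review for women who meet the diary criteria, and the start of run-in treatment ("Their first dose of placebo will be taken in the clinic").

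**Close of the window.** Section 10.5.4: "Any SAE occurring from Screening Visit 2 until 28 days after the last dose of IMP must be reported immediately". For women who permanently stop drug, Section 7.4 says "effort should be made to continue following the subject through to the end of scheduled visits for safety". Table 10-1 has a single row for AE and SAE recording, which runs to Week 16.

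**Outputs.** SAP Section 7.2 plans "Listing 16.2.7.7 Pre-Treatment Adverse Events (Safety Analysis Set") and puts Listing 16.2.7.2, all serious adverse events, on the same set. SAP Section 3.1 restricts that set to women who took at least one double-blind dose. Protocol Section 11.4 promises that all collected subject data will be listed.

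**The concern.** Withdrawing a consented woman from medication because the protocol prohibits it is something the trial does to her. If she is hospitalised as a result before Screening Visit 2, the plan as written does not make that an SAE. The stated reason for the late start is the absence of a full history. That helps to separate old conditions from new minor events, but it does not address serious events or events that follow a trial requirement. Section 10.5.3 itself accepts that an AE may be caused by a study procedure.

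At the other end, women who stop drug but agree to stay are followed for safety, and the immediate reporting duty can lapse weeks before their last visit. In the outputs, an SAE during the placebo run-in in a woman who is not randomised would be reported at the time but would be missing from both listings where a reader would look for it.

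**Working it through.** The plan gives no figure of its own to reproduce. The check is a comparison of sections plus day arithmetic.

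**1. Start of the window.**
- Consent comes at or before Screening Visit 1 (Table 10-1). The scheduled interval to Screening Visit 2 is Day -21 to Day -14, or 7 days, with a minimum of 6.
- Exclusion criteria 1 and 2 set washouts before Screening Visit 2 of 1 week (vaginal products), 4 weeks or 28 days (transdermal, non-hormonal), 8 weeks or 56 days (oral, intrauterine), 3 months or about 91 days (progestin implants, oestrogen-only injectables) and 6 months or about 183 days (oestrogen pellets, progestin injectables).
- If the washout begins at consent, the interval without AE or SAE reporting is at least that long. This is an assumption. The documents do not say how many women start washout at consent, and many may have stopped earlier or never used these drugs.
- Routes by which an event in this interval could still surface: medical history (Section 10.3.1); abnormalities found at Screening Visit 2, which go on the medical history page (Section 10.3.2); the recorded reason for any withdrawal after consent, with adverse event as a category (Section 7.4); and the AE review in Section 8.6.4. Women who fail the paper diary do not reach that review, and only limited data are collected on them.

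**2. Opening point.** One wording opens the period after the visit is complete (Sections 10.5.1 and 10.5.4). The other opens it from the time of the visit (Section 10.5.4, with the synopsis and Table 10-1 in line). The in-clinic run-in dose falls outside the first and inside the second.

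**3. End of the window.** SAE duty closes on day (last dose + 28). Gap = day of final visit − closing day, with the final visit on Day 113 (window Day 108 to Day 118) and negative gaps set to 0.

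| Last dose | Duty closes | Gap to Day 113 | Over Days 108–118 |
|---|---|---|---|
| Day 1 (extreme) | Day 29 | 84 days | 79–89 |
| Day 15 | Day 43 | 70 days | 65–75 |
| Day 29 | Day 57 | 56 days | 51–61 |
| Day 57 | Day 85 | 28 days | 23–33 |
| Day 84 (on-schedule completer) | Day 112 | 1 day | 0–6 |

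The completer row uses Section 9.4, where the last dose is taken the evening before the Week 12 visit. Women who leave the study altogether have an early termination visit within 14 days (Table 10-1, note b), which is inside the 28 days. The gap therefore concerns women who stop drug and stay.

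**4. Listings.** A woman who has an SAE in the run-in and is not randomised has taken no double-blind dose. She is not in the Safety Analysis Set, so she appears in neither Listing 16.2.7.2 nor Listing 16.2.7.7. The SAP does list run-in dosing on the Screen Analysis Set (Listing 16.2.5.1), so her capsules are listed and her adverse event is not.

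**The case against.** The strongest reply is that the start date is deliberate and explained, and that the plan loses less than it seems to.

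- A reader might infer that harm from washout is never recorded. The documents do not support that, because the routes in step 1 exist. What stands is that none of them classes the event as an AE or SAE or triggers safety reporting.
- A reader might set the washout lengths against 12 weeks of treatment and conclude that a third of that length (28/84 days), or about twice it (183/84 = 2.2), goes unrecorded. That holds only if washout starts at consent, and the longest case applies only to pellets and injectable progestin. Exclusion criterion 2 also lets women keep the non-hormonal drugs at a stable dose if prescribed solely for another disorder. Digoxin and the CYP3A4 and P-glycoprotein drugs are prohibited only from Screening Visit 2, with no earlier washout period stated.
- A reader might infer that late SAEs are lost. They are not: AEs are recorded in the eCRF to the final visit, and Listing 16.2.7.2 has no 28-day limit. What lapses is the 24-hour duty. A drug-based cut-off is defensible. With the half-life of about 15 to 20 hours in Section 5.1.3, 28 days (672 hours) is roughly 34 to 45 half-lives. The Table 10-1 row concerns recording, so it need not contradict a limit on immediate reporting. Even so, sites have to work that out for themselves.
- For completers, a 10-day gap can be built from a Week 12 visit on Day 81 (last dose Day 80, duty closes Day 108) and a final visit on Day 118. This is a corner case. Section 8.6.7 sets the final visit at 4 weeks ±5 days after the end of treatment, which gives at most Day 113 or 114 and a gap of 5 to 6 days.
- A run-in SAE missing from the listings is not unknown to the sponsor, since it must be reported within 24 hours, and Section 11.7 says screen failures will be described separately in the CSR. This is a point about outputs only.
- Section 10.5.4 refers to a Study Manual for detailed SAE instructions, which is not available here. It may narrow the gap in practice.

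**Conclusion.** The point holds in a limited form.

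1. Events between consent and Screening Visit 2, including serious ones after required medication withdrawal, are outside AE and SAE reporting. The interval is 7 days as scheduled and longer where washout extends it; how often is not stated.
2. The opening point is given in two incompatible ways, which differ on the in-clinic run-in dose.
3. The 24-hour SAE duty can end up to about 12 weeks before the final visit (84 days at the extreme, 70 days for last dose on Day 15) in women who stop drug and stay. The gap is about 1 day for on-schedule completers. Recording continues throughout.
4. Run-in events in women never given double-blind drug appear in neither safety listing.

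The documents do not support saying that sponsor and ethics committees would never learn of such harm. They support saying that the protocol text does not require it to be reported as a safety event. Efficacy analyses and treatment-emergent AE tables are not affected. The change is worth making because it concerns oversight of something the trial imposes and costs little.

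**What to change.** In Protocol Sections 10.5.1 and 10.5.4 and Table 10-1:
- Collect and report SAEs from informed consent, together with AEs attributed to required medication withdrawal or to a study procedure.
- State one opening point for all other AEs, worded so that it includes the in-clinic run-in dose, and use it in the synopsis as well.
- Run SAE reporting to the later of the final study visit and 28 days after last dose, so that Section 10.5.4 agrees with the continued safety follow-up in Section 7.4 and with the recording row in Table 10-1.

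In SAP Section 7.2, produce Listings 16.2.7.2 and 16.2.7.7 on the Screen Analysis Set.

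The cost is protocol and SAP wording and a few extra SAE and AE entries during screening and follow-up. No visit or procedure is added. Treatment-emergent tables do not change, because SAP Section 4.8.2 defines them by onset on or after the first randomised dose.

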### **Adverse Drug Reaction (ADR)**

All AEs considered to be untoward and unintended responses to an IMP related to any dose should be considered ADRs. The definition covers also medication errors and uses outside what is foreseen in the protocol, including misuse and abuse of the product. The phrase “responses to an IMP” means that a causal relationship between an IMP and an AE is at least a reasonable possibility, i.e., the relationship cannot be ruled out.

### **Serious Adverse Event (SAE)**

An adverse event that:

- Results in death
- Is life-threatening (i.e. the subject was at risk of death at the time of the event; it does not refer to an event which hypothetically might have caused death if it was more severe)
- Requires in-patient hospitalization or prolongation of existing hospitalization (see explanation below)
- Results in persistent or significant disability/incapacity
- Is a congenital anomaly/birth defect
- Is considered to be an important medical event

Based upon medical and scientific judgment, important medical events that may not be immediately life-threatening, or result in death or hospitalization, but may jeopardize the subject and/or may require intervention to prevent one of the other outcomes listed in the definition above may be considered a SAE.

Hospitalizations are defined as initial or prolonged admissions that include an overnight stay. Hospitalization or prolonged hospitalization for technical, practical or social reasons, in the absence of an adverse event is not an SAE and neither is attendance at an Emergency Room / Accident and Emergency Department that takes place in the evening or night and does not result in formal admission to the hospital.

### **Unexpected Adverse Drug Reaction**

An adverse reaction, the nature or severity of which is not consistent with applicable product reference safety information (Section 6.5 of the Investigator Brochure).

---

 The definition varies between regulatory jurisdictions

Reports which add significant information on the specificity, increase of occurrence, or severity of a known, already documented serious adverse reaction constitute unexpected events.

